Appendix 2: PPE Training Content Fidelity Evaluation

Directions: Score each measure with a value between 0-10 (0 is assigned if the topic is not discussed, 10 for discussed fully); total score is out of 100

1. Delivered information about the definition of PPE.

Score _____

2. Provided information about when to use PPE.

Score _____

3. Provided information about what types of PPE to use in different circumstances.

Score _____

4. Provide information about the appropriate fit of PPE.

Score _____

5. Provide do's and don'ts of glove use.

Score _____

6. Provided information about don PPE.

Score _____

7. Provided information about how and where to remove PPE.

Score _____

8. Provided information about how to safely store used PPE.

Score _____

9. Provided information about hand hygiene.

Score _____

10. Provided instruction and feedback during PPE practice session.

Score _____

TOTAL SCORE FOR TRAINING SESSION _____ / 10

Appendix 3: Combined CFIR and IMB Model Predicting PPE use

Part A. Example CFIR questions

Intervention Characteristics

1. Did you find the PPE training strategy acceptable?
2. How feasible do you think it will be to implement PPE use?
3. How do you think cost will impact your ability to implement PPE?

Inner Setting

1. How important do you think it is for healers to start using PPE during every injection?
2. Does the use of PPE clash with your current practices?

Outer Setting

1. How has your perception of the use of PPE been influenced by other healers in the Kukula Organization?
2. How have your patients influenced your use of PPE during treatments?

Process

1. Tell us about your experience being recruited and engaged in the PPE training?
2. How has your perception of the use of PPE been influenced by the leaders in the Kukula Organization.
- 3.

Part B. Questions from the Situated-Information Motivation Behavior Questions

Information (from the HIV Knowledge Scale, Ciampa et al. 2012) True/False/Do Not Know

1. A person can get HIV by getting an injection with a needle that was already used on someone else.
2. A person can get HIV by sharing blades.
3. A person can get HIV from mosquito bites.
4. A person can get HIV by sharing forks, spoons or cups with a person who has HIV.
5. A person can get HIV from a curse
6. Using gloves during injections will prevent HIV transmission.

Motivation (5-point Likert scale, strongly disagree to strong agree)

1. I believe I can use PPE every time I conduct an injection
2. I believe I am at high risk of HIV infection.
3. I believe PPE will prevent me from contracting HIV from my patients during treatments.

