Traditional healers face a risk of acquiring bloodborne pathogens from contaminated blood and body fluids. While most exposures for unbroken skin do not result in infection, risk of infection varies by the pathogen involved, the type of exposure, the amount of blood involved, and the amount of virus in the patient’s blood at the time of exposure.³⁰ The average risk of HIV infection after a needlestick or cut exposure to HIV-infected blood is 0.3%, and after exposure to eye, nose, or mouth is estimated to be 0.1%.³⁰ “Injections” result in substantial blood exposure- approximately 2 mL of blood per injection, which is in contact with a healer’s bare skin (primarily hands and arms- we find blood under healer fingernails after treatments- but as people touch their faces 23 times per hour, exposure to the mucus membranes is possible).³¹ Healers are often subsistence farmers (resulting in small cuts and abrasions on their hands from planting and harvesting, as well as from regular household activities, including preparing food and washing clothes). Furthermore, they have limiting access to potable water in their homes (thus, limited hand washing opportunities post-“injection”) exacerbating their risk of acquisition. In the Agincourt area (Figure 1), healers have an overall HIV prevalence of 30% (CI: 23%-37%) vs. 19% in the general population;³² in our previous study, healers who reported exposure to patient blood had 2.4-fold higher risk of being HIV-positive than those with no reported blood exposure (59% vs. 25%, respectively).²⁷

Low rates of PPE training and use can place healers at risk. PPE is defined as equipment or instruments (gloves, safety glasses, facemasks, respirators, etc.³³) worn to avoid and/or minimize exposure to hazards that could cause injuries or the spread of infection and illness. Use of PPE has been shown to be effective in reducing occupational exposures.³³⁻³⁵ Healers living with HIV may be perpetuating the epidemic, given their high HIV prevalence and their reluctance to attend clinical services (including HIV counseling, testing, and treatment). Healers may represent a reservoir of HIV-infected individuals with limited health facility contact. After acquiring HIV through their injection practices or elsewhere, healers are at risk of spreading the virus not only to their partners and children but also to other patients through further blood exposure, thus amplifying the effect of limited PPE/poor occupational hygiene.

2. Objectives

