Our intervention arm will receive the same training and educational outreach as the control arm, but with training and outreach conducted by a clinical team that includes healers who adopted and use PPE on their own (early adopters).³⁷⁻⁴⁰ Early adopters are people who identify a new behavior as innovative (i.e. use of latex gloves) and adopt this behavior before the majority of their colleagues. Used primarily in the Diffusion of Innovation Theory⁵² to explain adoption of new behaviors, we hypothesize that the strategy of engaging early adopting healers as trainers in collaboration with HCWs will increase peer pressure, perceived tension for change, participant self-efficacy, and acceptability of PPE use among healers who do not use any barrier to blood exposure. Early adopters can achieve this by highlighting relative advantages, compatibility with their role of a traditional healer and leader in the community, simplicity, and ease of trialability of using gloves with patients.⁵²

Participants will receive a baseline and end line (7 months post- training) HIV test (to detect any seroconversion events and to determine if those living with HIV are as motivated to use PPE as those who are HIV-negative). Participants will also complete baseline and end line surveys to assess their knowledge, motivation, and behavioral skills to determine the impact of training on the healer. Once a month, a study assistant will visit each healer to collect all used sharps and PPE; three times during the study the study assistant will also conduct observations of healers using PPE to determine if they are using it correctly post-training.

Healers and healer care workers who are selected, consent and contribute to the training of healers will be reimbursed for their transportation to the training venue and provided with a small token of appreciation (a voucher to a local store for R150) at the conclusion of the workshops.

6. Study Location

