The secondary outcome, proportion of injection events, will be analyzed in a manner identical to that of our primary outcome except the outcome will be the total number of skin-cutting events performed by the healer, regardless of the use of PPE. A negative binomial regression model will be fit using the number of overall procedures as an offset. While we will not specifically look at HIV seroconversion as a study outcome, we will assess healers' baseline and end line HIV status for ethical reasons. Historical data show that the one-year incidence rate of HIV seroconversion is 1.7%. Since the incidence rate is low, we will likely not have adequate power to see a difference between intervention arms, but this information will allow us to appropriately power our subsequent R01 trial.

A separate analysis will assess each strategies' effect on PPE self-efficacy, PPE knowledge/skills, and accurate risk assessment post-training. We will explore whether the intervention effects on these measures differ by a) trainer fidelity to the intervention and/or trainer identity (healer vs. clinician), respectively. These analyses will provide quantitative data to revise and refine, as needed, the intervention for evaluation in a large RCT effectiveness study as a means of improving prevention engagement while reducing stigma.

8. Ethical Considerations

Recruitment and Consent

Aim 1: *Traditional healers* from the target community will be recruited via two strategies: (1) Healers in target catchment area are currently being mapped by two students (one from Vanderbilt and one from University of Witwatersrand). The healers are providing their address/location and contact information (phone numbers, contact for other family members) for use in future activities (including research endeavors). The healers will be contacted and given general information about the proposed study. All healers will be invited to community meetings where more information about the study procedures and aims will be provided. (2) The Kukula Traditional Healers association- the primary healer organization in the region- will hold 3 meetings to recruit healers interested in participating. Healers who express interest will be given the option for dates/locations where we will conduct recruitment fairs or the option to have a study assistant visit them at home. All recruitment will be conducted in a private room or at the home of the healer (as per the participants preference).

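### Two of the three printed Motivation items ask about acquiring HIV and do not fit healers who know they have it, and the only own-risk item measures perceived rather than accurate risk

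*Combined protocol and SAP*

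**What the plan says.** Section 5 (Methods, Study Procedures, Aims 2 & 3) gives two purposes for the baseline and end line HIV tests. One is to detect seroconversion. The other is "to determine if those living with HIV are as motivated to use PPE as those who are HIV-negative". The same paragraph states: "Participants will also complete baseline and end line surveys to assess their knowledge, motivation, and behavioral skills".

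The only items headed Motivation are in Appendix 3, Part B. There are three, each answered on a five-point agreement scale. Item 1 asks whether the healer feels able to use PPE at each injection. Item 2 turns to the healer's own risk: "I believe I am at high risk of HIV infection". Item 3 concerns the protective effect of PPE and is worded as follows: "I believe PPE will prevent me from contracting HIV from my patients during treatments".

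No skip by HIV status, no not-applicable choice and no scoring rule is printed.

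Section 7 (Data Analysis, Aim 3) plans a separate analysis of each strategy's effect on "PPE self-efficacy, PPE knowledge/skills, and accurate risk assessment post-training". Section 5 describes the underlying construct as the healer's accurate assessment of the risk of bloodborne illness and places it under motivation.

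The inclusion and exclusion criteria in section 4 do not mention HIV status. The background section puts HIV prevalence among healers in the area at 30%, with an interval from 23% to 37%.

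**The concern.** A comparison between two groups needs items that mean the same thing in both. Items 2 and 3 ask about becoming infected with HIV, and one of the two groups is defined by already having it. For those respondents the grouping variable changes what the question means, and a larger sample does not repair that.

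The second problem is the risk measure. An answer can be called accurate only against some reference. Item 2 asks for agreement with a statement about HIV risk in general, and nothing in the plan says which answer is right for which healer.

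The background section presents healers living with HIV as a possible source of onward transmission. Section 7 says the separate analysis will help refine the intervention for a larger trial. An artefact of wording could therefore be carried forward as a finding about this group.

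**Working it through.** **Inputs.** 61 healers per arm, 122 in total (section 4, sample size for Aim 3). HIV prevalence among healers 30%, interval 23% to 37% (background). Three Motivation items on a 5-point scale (Appendix 3, Part B).

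**The plan's own figure.** For a difference of 0.20, SD 0.39, two-sided alpha 0.05 and 80% power, the normal approximation gives n per arm = 2 × (1.960 + 0.842)² × (0.39/0.20)² = 59.7, rounded up to 60. The exact two-sample t-test gives 60.67, rounded up to 61, with power 80.22% at 61. This matches Table 1. The sample size is not in dispute; it only sets how many healers answer the items.

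**Item by item, for a healer who knows he or she has HIV.**

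| Item | Content | Coherent answer? |
|---|---|---|
| 1 | Can use PPE at every injection | Yes; measures self-efficacy |
| 2 | At high risk of HIV infection | No; the event has already happened |
| 3 | PPE prevents me from contracting HIV | No, unless read as a general belief about PPE |

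The rest of the protocol shows that the gap is avoidable. The Appendix 4 checklists offer an N/A score. The last Information item in Appendix 3 asks about gloves and HIV transmission without reference to the respondent's own status.

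**How many healers.** Affected = 122 × prevalence × k, where k is the fraction of healers living with HIV who know their status.

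- k = 1: 122 × 0.30 = 36.6, about 37 (about 18 per arm); 122 × 0.23 = 28.1; 122 × 0.37 = 45.1.
- The documents give no k. As an assumption, k = 0.5 at 30% prevalence gives 36.6 × 0.5 = 18.3, about 18.

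The rapid-test item in Appendix 1 says known positives are not re-tested, so those healers know their status when they answer. Others may learn it from the baseline test, which would bring k closer to 1 at later surveys.

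**How large a distortion.** If true motivation is equal and a fraction f of healers living with HIV shift their answer to an item by s points because of its wording, the spurious group difference on that item is f × s. The plan gives neither f nor s. Assuming f from 0.25 to 1 and s from 0.5 to 1, the difference runs from 0.25 × 0.5 = 0.125 to 1 × 1 = 1.0 point per item. The sign is also open: a healer living with HIV may disagree with item 2 because infection can no longer occur, or agree with it because it has.

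**Risk assessment.** The outcome in section 7 differs from item 2 in three ways. The construct is bloodborne illness, and the item covers HIV only. The exposure of interest is patient blood, and the item covers any source. The outcome is accuracy, and the item records a belief with no correct answer attached. No other printed item asks about the healer's own risk.

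**The case against.** The case on the other side is substantial, and most of it limits the size of the point rather than removing it.

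- **No total is planned.** A reader might sum the three items (range 3 to 15), assume that HIV-negative healers average 4 and all healers living with HIV answer 1, and infer a false gap of 3 to 6 points. The plan does not sum these items; its only summed survey scores belong to Aim 1. Even on a hypothetical total with SD 2 to 3 and groups of 37 and 85, the result follows the assumptions. A shift of 0.5 point on items 2 and 3 in 25% of healers living with HIV (total 2 × 0.5 × 0.25 = 0.25) gives a 7% to 10% chance of a false significant difference. A shift of 1 point in all of them (total 2.0) gives 92% to nearly 100%.
- **Direction.** A reader might infer that healers living with HIV must look less motivated. The documents do not support that, because agreement with item 2 is also possible and item 3 can be read as a belief about PPE.
- **Prevalence is not known status.** This stands; 37 is an upper figure at 30% prevalence.
- **Reversal by successful training.** A reader might infer that a better strategy lowers agreement with item 2 because gloved healers are at less risk. That could occur at end line. It is hard to sustain at the survey immediately after training, when little changed glove use can have accrued.
- **Status of the comparison and the list.** Section 7 gives no model for an analysis by HIV status. Glove use and item 1 can be compared whatever the wording of items 2 and 3. Part B might also be an excerpt, although only Part A is labelled as examples.

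What survives is that the comparison is a stated purpose of testing, two of the three printed items do not suit one of its groups, and accuracy has no definition.

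**Conclusion.** The point holds as a limited instrument defect. Any comparison of motivation by HIV status that uses item 2 or 3, singly or combined, may be distorted by the wording, by an amount and in a direction that the documents do not determine. Up to about 37 of 122 healers are affected at 30% prevalence (28 to 45 over the quoted interval), assuming that all of them know their status, and fewer otherwise. As printed, item 2 yields perceived HIV risk and cannot stand for accurate assessment of bloodborne risk.

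This rests on the printed Part B being the full list of Motivation items. The primary glove-use outcome is not affected. Randomization should roughly balance HIV status between arms, so the distortion bears on the comparison by HIV status more than on the comparison of strategies. The separate question of what counts as accurate applies to the comparison of strategies as well.

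**What to change.** 1. **Reword before baseline**, so that both items apply to every healer and concern injections. For example, item 2: *Doing an injection without gloves exposes me to infections carried in the patient's blood.* Item 3: *Gloves will protect me from infections carried in my patients' blood.* Item 2 should speak of exposure and not of high risk. The background section quotes average HIV risks of 0.3% after a needlestick or cut and 0.1% after eye, nose or mouth exposure, so agreement with a high-risk statement would not be clearly accurate.
2. **If the present items are kept**, analyse them only in HIV-negative healers and state how unknown, refused and indeterminate results are classified.
3. **Base the comparison by HIV status** on item 1, the status-neutral items and recorded glove use, and name it in section 7.
4. **In section 7**, either report item 2 as perceived risk, or score accurate risk assessment in HIV-negative healers against their own recorded glove use. The second option needs accrued records and so fits end line better than the survey immediately after training.

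The cost is two reworded items and a few sentences in section 7. The downside is some loss of comparability with any earlier use of the present items. The sample size does not change.

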Appendix 4: Behavior Assessment of PPE Skills at the completion of the training sessions

Hand Hygiene Checklist

Score each method of hand hygiene based on the tasks indicated: done - 1; not done or done incorrectly - 0; not applicable or not assessed - N/A.

Method	Task	Status	Notes
Alcohol-Based Hand Rub	ABHR is appropriate choice of hand hygiene for the situation		
	Remove inappropriate jewelry		
	Use enough alcohol rub to thoroughly wet both hands		
	Spread product over all surfaces of hands (palms, between fingers, fingertips, back of hands and wrists)		
	Rub hands for at least 15s or until product is dry		
Alcohol-Based Hand Rub Subtotal			
Soap and Water	Remove inappropriate jewelry		
	Wet hands and apply soap		
	Lather all surfaces of hands for 15s (palms, between fingers, fingertips, back of hands and wrists)		
	Rinse all sides of hands under running water		
	Dry hands with paper towels		
	Turn off taps with paper towels		
Soap and Water Subtotal			
TOTAL SCORE			

Donning Checklist

Indicate the personal protective equipment (PPE) required for the scenario then number them in the table as the user dons each item. Score the use of each item based on the tasks indicated: done - 1; not done or done incorrectly - 0; not applicable or not assessed - N/A.

PPE
Required: _____

User's PPE sequence↓	Task	Status	Notes
Hand Hygiene #_____	Hand Hygiene was performed		
	The choice of Hand Hygiene was appropriate		
Gown #_____	Choose correct type of gown (if available)		
	Put gown on with the opening at the back		
	Tie neck and waist ties		
Mask #_____	Chosen mask is appropriate face protection for the situation		
	Place mask over the nose and mouth		
	Mold metal strip to nose		
	Secure elastics or ties		
Eye Protection #_____	Put on		
	Adjust to fit (e.g. face shield should fit over brow)		

Gloves # _____	Remove inappropriate jewellery		
	Choose correct type of gloves (if available)		
	Choose well-fitting gloves		
	Put on gloves (if gown is worn, place gloves over gown cuffs)		
	Subtotal		
PPE Selection Score (Add 5 points for each required item that was selected and subtract 5 points for each necessary item that was not selected.)			
PPE Donning Sequence Score (No points if any sequence errors. Award 5 points for each required item/step in a perfect sequence - as listed in table.)			
TOTAL SCORE			

Doffing Checklist

Score the use of each item based on the tasks indicated: done - 1; not done or done incorrectly - 0; not applicable or not assessed - N/A.

Number of **items** to be doffed: _____

Number of hand hygiene **steps** required: _____

User's PPE sequence	Task	Status	Notes
Gloves # _____	Remove the first glove using glove-to-glove technique		
	Remove the second glove using skin-to-skin technique, turning gloves inside out		
	Drop into garbage without touching bin		
Gown # _____	Unfasten the ties or Velcro and peel gown away from the neck		
	Remove the gown slowly, pulling away from the body, without touching the outside or contaminating clothing		
	Roll the gown into a bundle inside-out or fold dirty-to-dirty		
	Discard the gown in appropriate receptacle		
Hand Hygiene # _____	Hand Hygiene was performed		
	The choice of Hand Hygiene was appropriate		
Eye Protection # _____	Remove goggles/visor using the earpiece/band		
	Lift away from the face without touching the face/eyes/nose		
	Discard in the garbage/If reusable, clean and disinfect		
Mask # _____	Undo the ties or elastics without touching the front of the mask		
	Holding the ties or elastics, lift mask away from the face		
	Discard mask in the garbage		
Hand Hygiene # _____	Hand Hygiene was performed		
	The choice of Hand Hygiene was appropriate		
Subtotal			

Doffing Sequence Score (No points if any sequence errors. Award 5 points for each required item/step in a perfect sequence - as listed in table.)	TOTAL SCORE
---	--------------------

PPE Handling (Correct and careful use of PPE)					
N/A	1	2	3	4	5
Incorrect donning/doffing of PPE with critical errors Mostly correct donning/doffing of PPE with few non-critical errors and/or correction of critical errors Perfectly correct donning/doffing of PPE with no errors					
Flow of Operation (Forward planning and continuity of procedure)					
N/A	1	2	3	4	5
Demonstrated no forward planning and appeared unsure of next steps with irregular progression of actions Demonstrated some forward planning and anticipation of the situation with steady progression of actions Demonstrated obvious forward planning and anticipation of the situation with effortless progression of actions					
Self-Contamination (Avoidable/unnecessary contamination of PPE user during or after care activities)					
N/A	1	2	3	4	5
Indiscriminately contaminated self during and/or after client/patient care activities Made appropriate corrections for self-contamination during and/or after client/patient care activities Perfect technique employed to prevent self-contamination both during and after client/patient care activities					
Contamination of Environment (Contamination of environmental surfaces during or after care activities)					
N/A	1	2	3	4	5
Touched environmental surfaces inappropriately putting others at risk of transmission of microorganisms through contaminated surfaces Touched environmental surfaces inappropriately but corrected errors to prevent transmission of microorganisms through contaminated surfaces Did not touch environmental surfaces inappropriately, preventing risk of transmission of microorganisms through contaminated surfaces					
Cross-Contamination (Contamination of client/patient due to contaminated PPE used between care activities and procedures)					
N/A	1	2	3	4	5
Indiscriminately caused cross-contamination of PPE and/or client/patient between care activities Made appropriate corrections for cross-contamination of PPE and/or client/patient between care activities Appropriate technique used throughout the procedure to prevent cross-contamination of PPE and/or client/patient between care activities					
TOTAL SCORE
